Compañeros en Salud (CES) is an affiliate project of Partners in Health, an international non-governmental organization with extensive experience in the use of CHW interventions to help patients to manage chronic disease. Since February 2012, CES has been working in the Sierra Madre region of rural Chiapas, Mexico, in partnership with the local Ministry of Health, to rehabilitate and staff existing government primary care clinics. Each community's clinic is staffed by one CES project physician year-round. CES activities span the range of primary care, but the focus of the project is in the prevention, detection, diagnosis and management of NCDs. At the time of study initiation, CES operated in six rural communities; they expanded to four additional communities after the study began (two were added August 2014, and two more February 2015). Routine care for NCDs is based on national guidelines and consists of monthly in-clinic visits by primary care physicians. Routine care of major depressive disorder includes monthly in-clinic visits, psychoeducation, and daily medications when indicated.

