## ACCOMPANEERS STUDY DETAILED PROTOCOL

### c. Statistical methods

Patients will be categorized as having adequate adherence based on pre-determined cutoff points from the standardized assessments. Hypertensive patients with a systolic blood pressure of <140 mmHg and a diastolic blood pressure of <90 mmHg (<130 mmHg and <80 mmHg, respectively, in patients with comorbid diabetes), and diabetic patients with a hemoglobin A1c of less than 7.0% will be defined as having achieved disease control. The stepped wedge crossover study design allows for pre- and post-intervention comparisons with the added benefit of accounting for time-related bias. Due to the small number of communities and expected variation in the number of participants per community, we will use random-effects generalized estimating equations with “sandwich” variance estimates to conduct individual-level analyses adjusted for clustering at the community and individual levels.

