### d. Power analysis (e.g. sample size, evaluable subjects, etc)

With an average of 32 patients per community with diabetes or hypertension across the eight study communities, an 80% participation rate, and eight data collection periods per community (baseline, 3 months, 6 months, 9 months, and 12 months), we will have greater than 80% power to detect a 40% change in adherence, assuming a 50% of individuals meet the definition of good adherence prior to the intervention. These estimates are intentionally conservative, with lower baseline rates of adherence, greater improvements in adherence, and greater program participation observed in our pilot community.

With 50 patients with depression total in communities “E”–“H”, utilizing a paired t-test, and anticipating a baseline adherence of 50%, we will have 90% power to detect a 40% improvement in adherence, an effect similar to that seen in the preliminary results from communities “A” – “D”.

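### The analysis sentence leaves open the sandwich's clustering unit, any community-by-round correlation, a small-sample correction and the model family; without a correction, each reading can give intervals that are too short.

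*Combined protocol and SAP*

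**What the plan says.** One sentence in section VI.c carries the whole model: "we will use random-effects generalized estimating equations with “sandwich” variance estimates", to conduct "individual-level analyses adjusted for clustering at the community and individual levels". It gives the small number of communities and their unequal size as reasons for this choice. It does not give a link function, a working correlation, the unit on which the sandwich is clustered, a small-sample correction or a reference distribution. The design "allows for pre- and post-intervention comparisons with the added benefit of accounting for time-related bias", but no round term is written out.

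Section VI.d supplies the size: "With an average of 32 patients per community with diabetes or hypertension across the eight study communities", and "an 80% participation rate". It states no ICC, alpha or sidedness. The same patients are surveyed every three months (V.e), and the programme reaches new villages once every three months in random order (IV.c), in two sets of four communities. Section I.b says that each community's "clinic is staffed by one CES project physician year-round".

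**The concern.** Community and participant effects alone make two patients of one community equally correlated whether they are surveyed in the same round or 21 months apart. Patients here share one clinic and one physician, so something that moves the whole community in a single round is plausible. A model without a community-by-round component counts that movement as separate noise in each patient and averages it away over about 26 patients, although it is a single event. The sandwich might repair this, but whether it does depends on its clustering unit, which is not stated. If the unit is the community, a different problem arises, because the uncorrected estimator needs many clusters and there are eight.

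The words "we will use random-effects generalized estimating equations" add a second ambiguity. A random-effects logistic model estimates a participant-specific odds ratio and a GEE a population-average one. For yes/no adherence the reported effect could depend on which half of the label the analyst follows.

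At stake are the interval widths and false-positive rates for Aims 1 to 3, and the meaning of the odds ratio if one is reported.

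**Working it through.** **Inputs from the protocol.** Eight communities; 32 × 0.80 = 25.6 participants each, about 205 in all; baseline adherence 50%; a 40% change, read as relative (0.50 × 1.4 = 0.70). Rounds: VI.d says "eight data collection periods per community (baseline, 3 months, 6 months, 9 months, and 12 months", so it states eight and lists five. Eight fits 21 months of follow-up (21/3 + 1 = 8). I used eight and checked five.

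**Assumed, because not stated.** Two-sided 5%; fixed round effects within each set of four; one community switching per round; no dropout; variance σ² = (0.25 + 0.21)/2 = 0.23; 40% of within-community variance persistent in the participant. ICC is the correlation of two patients of one community in the same round. CAC (community autocorrelation) is the ratio of the between-round to the within-round correlation.

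**1. The plan's own figure.** Two independent groups of 102 at 50% and 70% give power of about 84%, and 205 before against 205 after gives 98.7%. A stepped wedge GLS with no community-by-round effect gives over 99%. The stated bound of more than 80% is met. The plan's own calculation cannot be recovered without its alpha and ICC.

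**2. Model-based inference without the community-by-round term.** Split the variance into community τ² = σ²·ICC·CAC, community-by-round γ² = σ²·ICC·(1 − CAC), participant α² = 0.4σ²(1 − ICC) and residual ε² = 0.6σ²(1 − ICC). The round-specific variance of a community mean is truly γ² + ε²/m. The two-level model takes it as (γ² + ε²)/m.

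For ICC 0.05 and CAC 0.8: γ² = 0.23 × 0.05 × 0.2 = 0.0023; ε² = 0.6 × 0.23 × 0.95 = 0.1311.
- True: 0.0023 + 0.1311/25.6 = 0.00742.
- Modelled: 0.1334/25.6 = 0.00521.
- Root of the ratio: √1.424 = 1.19.

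The full GLS gives the same ratio, 1.19: SE 3.7 points reported against 4.4 actual (3.9 against 4.6 if σ² = 0.25). Error = 2[1 − Φ(1.96 × reported SE/actual SE)] = 2[1 − Φ(1.96/1.19)] = 10.0%.

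| ICC | CAC | actual/reported SE | error at nominal 5% |
|---|---|---|---|
| 0.02 | 0.8 | 1.08 | 6.9% |
| 0.05 | 0.9 | 1.10 | 7.5% |
| 0.05 | 0.8 | 1.19 | 10.0% |
| 0.05 | 0.5 | 1.42 | 16.7% |
| 0.10 | 0.5 | 1.75 | 26.2% |

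At ICC 0.10, CAC 0.5 and a participant share of 0.7, the error is 37%. With five rounds the ratios barely change (1.19 and 1.40 in rows three and four).

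**3. Effect of the sandwich unit.** Simulated error with Gaussian outcomes, eight communities, eight rounds, ICC 0.05 and 2,000 runs (Monte Carlo SE near 16% is √(0.16 × 0.84/2000) = 0.8 points):

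| Inference | CAC 1 | 0.9 | 0.8 | 0.5 |
|---|---|---|---|---|
| Model-based | 5.2% | 7.2% | 10.0% | 17.6% |
| Sandwich on participants | 5.6% | 7.4% | 10.4% | 18.4% |
| Sandwich on community, uncorrected, z | 16.3% | 15.8% | 16.0% | 18.0% |

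The participant-level sandwich follows the model-based rate. The community-level sandwich is nearly flat in CAC and already inflated at CAC 1, so its problem is the number of clusters. With 80 communities (ICC 0.05, CAC 0.5) it falls to 5.7%, while model-based inference stays at 17.3%. With eight communities, a Mancl–DeRouen correction and t on 6 degrees of freedom, it is about 1.5% to 2.3%.

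**4. The two odds ratios.** For 50% to 70% the population-average odds ratio is (0.7/0.3)/(0.5/0.5) = 2.33. A logistic model with a normal participant intercept that reproduces the same two proportions needs an odds ratio of about 3.3 at participant ICC 0.4 and 4.4 at 0.6 (logit scale).

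**5. Power with the term included** (eight rounds, 50% to 70%, normal approximation): 99.5% at ICC 0.05/CAC 0.8; 96.7% at 0.05/0.5; 87.1% at 0.10/0.5; 66.6% at 0.20/0.5.

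**The case against.** The best defence is the sandwich itself. Clustered on community, it allows any correlation within a community, including within a round, and the community-by-round term need not be modelled. This stands. A reader might infer that the missing term by itself makes the intervals too short, or that this is a separate matter from small-sample correction. The documents do not support either, because they specify sandwich variance and do not say on what unit.

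A reader might also infer that, with one community crossing per step, a one-round swing cannot be told apart from the intervention effect. That goes too far. The other communities in the set are surveyed in the same round, the programme continues through later rounds, and there are two sets. A swing adds noise (4.4 against 3.7 points in the worked case); it does not make the effect unidentifiable.

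Three further objections stand as limits. The documents report no physician turnover or supply failure, so the size of any swing is assumed. They name no link function and do not promise an odds ratio, and the two odds ratios do not arise for identity-link analyses of HbA1c, blood pressure or PHQ-9. The 70% target is one reading of the 40% change; an absolute reading gives 90%.

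The defence does not rescue the sentence as written. A community-level sandwich without a correction is unreliable with eight clusters, and the plan cites the small number of communities without adding one.

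**Conclusion.** The specification is incomplete in a way that affects inference. Under model-based or participant-level sandwich inference, the omitted community-by-round correlation shortens intervals: about 7% to 17% error for ICC 0.02 to 0.05 and CAC 0.8 to 0.5, more in extreme cases, and essentially none if CAC is 1. Under an uncorrected community-level sandwich the error is about 16% to 18%, and the cause is eight communities. So at ICC 0.05 and CAC 0.9 or below, every uncorrected reading exceeds 5%.

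These figures rest on assumed correlations and a linear, Gaussian approximation. IV.c labels the second set E through G and VI.b labels it E to H; with seven communities the SE ratios are nearly the same and power is lower (78.2% at ICC 0.10/CAC 0.5). A reader might infer that the trial is underpowered once the term is added. With eight communities and 50% to 70%, the stated bound fails only at high ICC with low CAC.

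**What to change.** Replace the sentence in VI.c with one fully specified model, with fixed round effects within each set of four communities, and choose between:

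- a mixed model with random effects for community, community-by-round and participant, with small-sample degrees of freedom; or
- a GEE with a block-exchangeable working correlation (separate within-round, between-round and within-participant terms), a sandwich clustered on community, a small-sample bias correction such as Mancl–DeRouen, and a t reference.

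Changing the working correlation alone is not enough for the GEE, because it does not remove the few-cluster bias. For yes/no outcomes, state the link and report a standardised risk difference, so that the result does not depend on the model family and is on the same scale as the 50% baseline in VI.d. State the ICC and CAC assumed for the power calculation.

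The cost is SAP wording and one additional variance or correlation parameter. Intervals will be somewhat wider when communities drift between rounds. The corrected sandwich may be conservative with eight communities (1.5% to 2.3% at nominal 5%), which costs some power.

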### d. Power analysis (e.g. sample size, evaluable subjects, etc)

With an average of 32 patients per community with diabetes or hypertension across the eight study communities, an 80% participation rate, and eight data collection periods per community (baseline, 3 months, 6 months, 9 months, and 12 months), we will have greater than 80% power to detect a 40% change in adherence, assuming a 50% of individuals meet the definition of good adherence prior to the intervention. These estimates are intentionally conservative, with lower baseline rates of adherence, greater improvements in adherence, and greater program participation observed in our pilot community.

With 50 patients with depression total in communities “E”–“H”, utilizing a paired t-test, and anticipating a baseline adherence of 50%, we will have 90% power to detect a 40% improvement in adherence, an effect similar to that seen in the preliminary results from communities “A” – “D”.

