## ACCOMPANEERS STUDY DETAILED PROTOCOL

CES has conducted several community outreach programs to identify community members living with NCDs, including an active case finding program consisting of door to door visits at every home in the catchment area of CES clinics. Screening activities include a risk factor questionnaire for diabetes and hypertension as well as in-home blood pressure screening and referral for blood glucose and blood pressure screening when indicated. They also include screening for depression, and referral for diagnosis in the clinic when indicated. This approach allows diagnosis of chronic disease in an environment in which patients traditionally seek care only for acute illness, and has allowed for diagnosis of a majority of patients living in project communities with hypertension or diabetes. These patients have been started on treatment and are being followed by CES physicians in the clinics in a monthly basis.

In July 2012, CES piloted a CHW program utilizing CHWs locally called “Acompañantes” (aka. Accompaneers, in English) in one of its project communities to augment care of patients with NCDs. Accompaneers are lay health workers, nominated by their communities, who bridge the gap between project clinics and patients, improving patients’ understanding of NCDs, their treatments, and the importance of adherence to therapy. CES physicians offer participation in the Accompaneer program to patients diagnosed with hypertension, diabetes, and depression, in addition to other diseases requiring daily therapy. Accompaneers conduct regular home visits to educate patients, support medication adherence, identify barriers to accessing care, and ensure the timely supply of medications. They are trained using a series of standardized educational sessions, and CES supervisors provide oversight. To date, over 80% of patients with NCDs have opted for the support of an Accompaneer. In our pilot community, the CES physician report fewer treatment interruptions, greater disease literacy and improved clinic attendance in the Accompaneer pilot community.

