**b. Study endpoints**

Study timeframe: The study, including the enrollment period and baseline data collection, will run for approximately 44 months in total. Baseline data collection and participant enrollment will occur concurrently prior to study initiation; this period is anticipated to take approximately one month. The study will then run for the subsequent continuous 21 months in the original communities, then conclude. Upon completion of data collection in the original four communities ("A" – "D"), baseline data collection and participant enrollment in the four remaining communities ("E" – "H") will commence; this period is expected to take approximately one month. Thereafter, the study will run in these communities for the subsequent continuous 21 months.

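### Does citing a lower pilot baseline undermine the claim that the power estimate is conservative?

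*Combined protocol and SAP*

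**What the plan says.** Section VI.d (Power analysis) sets out the inputs for patients with diabetes or hypertension: "With an average of 32 patients per community with diabetes or hypertension across the eight study communities", with "an 80% participation rate". The power claimed is above 80% "to detect a 40% change in adherence, assuming a 50% of individuals meet the definition of good adherence prior to the intervention". The section does not say whether the 40% is relative (50% to 70%) or in percentage points (50% to 90%), and it gives no alpha, intraclass correlation or within-patient correlation.

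It then describes the margin: "These estimates are intentionally conservative, with lower baseline rates of adherence, greater improvements in adherence", followed by greater program participation, all attributed to the pilot community. No pilot adherence rate is given there. The pilot account in Section I.b says that "the CES physician report fewer treatment interruptions, greater disease literacy and improved clinic attendance", and that over 80% of patients with non-communicable diseases chose to have an Accompaneer. It gives no before and after adherence figures either.

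The outcome is binary at the patient level (VI.c): "Patients will be categorized as having adequate adherence based on pre-determined cutoff points from the standardized assessments".

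**The concern.** The sentence invites the reader to believe there is power to spare because real baseline adherence is probably below the assumed 50%. With the effect held at a relative 40%, the opposite is true. The target difference is 0.4 times the baseline: 20 points from 50%, 16 from 40%, 12 from 30%. The binomial variance changes little over that range, so the smaller difference dominates and power falls. On the percentage-point reading the variance also rises as the baseline moves down from 50% to 30%, so the direction is again unfavourable, though only slightly.

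If this mattered, a null primary result might be read as evidence against a 40% gain when the study had less power for that gain than the plan suggests. The sentence would also be using pilot evidence of a low baseline as reassurance when that evidence called for a check.

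**Working it through.** **Inputs from VI.d.** Eight communities × 32 = 256 patients; × 0.80 = 204.8 participants, or 25.6 per community and 102.4 per condition if split in two. Baseline 50%; change 40%; power above 80%.

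**Assumed, because the plan is silent.** Two-sided alpha 0.05; intraclass correlation (ICC) 0.01 to 0.20; both scales for the 40%.

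**1. The plan's own figure.** Two-proportion power, ignoring clustering and repeated visits, with p̄ = (p1 + p2)/2 and d = p2 − p1:

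power = Φ{[d√n − 1.96√(2p̄(1−p̄))] / √(p1(1−p1) + p2(1−p2))}

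For 50% to 70%, n = 102.4: [0.2 × 10.119 − 1.96 × 0.6928] / 0.6782 = 0.982, so power is 83.7%. For 50% to 90% it exceeds 99.9%.

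A Hussey-Hughes stepped-wedge calculation (normal approximation; eight communities, two per step; variance p̄(1−p̄); five or eight periods) gives 96.9% to 99.4% on the relative reading over ICC 0.01 to 0.20, and more than 99.9% on the points reading. All are consistent with a claim of more than 80%. Because that claim is a lower bound and the method is not given, no exact figure can be matched.

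**2. Lower the baseline with the 40% held fixed.** Number per group for 80% power:

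n = [1.96√(2p̄(1−p̄)) + 0.8416√(p1(1−p1) + p2(1−p2))]² / d²

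| Baseline | Relative 40% | n | 40 points | n |
|---|---|---|---|---|
| 50% | to 70% | 93 | to 90% | 20 |
| 40% | to 56% | 152 | to 80% | 23 |
| 30% | to 42% | 250 | to 70% | 24 |

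On the relative scale the requirement grows by 152/93 = 1.6 and 250/93 = 2.7. On the points scale it barely moves. It is back to 20 at a 10% baseline and falls to 18 at 5%, so there the direction reverses.

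**3. Hold the odds ratio fixed instead.** 50% to 70% is an odds ratio of 2.33. The same odds ratio takes 40% to 60.9% and 30% to 50%. Unclustered power with 102.4 per condition is 83.7%, 85.3% and 83.7% at baselines of 50%, 40% and 30%: essentially no loss.

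**4. Stepped-wedge power, relative 40%.** Hussey-Hughes, ICC 0.05:

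| Baseline | Five periods | Eight periods |
|---|---|---|
| 50% | 96.9% | 98.6% |
| 40% | 85.1% | 90.4% |
| 30% | 64.9% | 72.2% |

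A fuller model adds patient-level correlation (share 0.3), cluster autocorrelation of 0.8 to 1, two waves with separate period effects, and either a normal or a t reference with 6 degrees of freedom, for 205 or 256 patients. At a 40% baseline it keeps 80% in 11 of 12 combinations (the exception is 78.8%). At 30% it falls below 80% in 8 of 12. That last count depends heavily on the assumed patient share: 11 of 12 at 0.1, 3 at 0.5 and 2 at 0.6.

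**5. What the other two reasons contribute.** To match the power of 50% to 70%, a 40% baseline must reach 60.4% (20.4 points, a 51% relative gain) and a 30% baseline must reach 50% (20.0 points, a 67% relative gain). Raising participation from 80% to 100% at a 40% baseline lifts unclustered relative-scale power only from 63.2% to 72.9%. Larger gains can therefore offset the lower baseline; fuller participation alone does not.

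**The case for a change.** The strongest case for a change is that the lower baseline is listed as a reason in its own right. On the relative scale it points the wrong way, and the larger gains that might offset it cannot be checked because no pilot rates are given. The relative reading is also the more natural one: the simple calculation gives 83.7%, which suits a claim of more than 80% better than a figure above 99.9% would. The repair would cost only wording and a small table.

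The point about direction stands: a lower baseline alone does not make the estimate conservative on either of the two plain readings, for baselines between 10% and 50%. What does not follow is that the label is false. The sentence does not hold the gain at 40%; it says the pilot gain was larger. A lower start with a gain of about 20 points or more is a coherent reason to call 50% and 40% cautious. The documents neither confirm nor contradict it. The same section also says that a 40% improvement in adherence among patients with depression resembles preliminary results from communities A to D.

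A further untidiness in the same sentence is clerical. It gives "an 80% participation rate, and eight data collection periods per community (baseline, 3 months, 6 months, 9 months, and 12 months", so five visits are listed for eight periods. VI.b says: "The study will then run for the subsequent continuous 21 months in the original communities, then conclude". Quarterly visits over 21 months give 21/3 + 1 = 8, so the count is right and the list is short.

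**Conclusion.** The observation is correct but calls for no change. One of three reasons in a justification sentence does not support the label by itself. The power claim it comments on, above 80% at a 50% baseline, is not shown to be wrong: the eight-community calculations give 83.7% without clustering and 96.9% or more in the Hussey-Hughes model.

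A material shortfall needs several things together: the relative reading, a true baseline near 30%, a gain no larger than 40%, and particular values of ICC, patient-level correlation and degrees of freedom. None of those values, nor the 30% baseline, is in the documents. At a 40% baseline the stepped-wedge models almost always keep 80%. On the points scale, or at a constant odds ratio, nothing practical is lost.

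Removing the clause would not alter recruitment, which rests on the patients available in eight communities, nor the visits, the outcome definition or the model. A null result would in any case be judged from its estimate and confidence interval, which show directly whether a gain of the planned size is excluded. The unstated scale, alpha and correlations are reporting detail that an analyst can supply, and the short visit list is a slip.
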